#### 4.2 Secondary Objectives:

- To quantify sensitivity, specificity, positive and negative predictive values of both IGRAs and conventional diagnostic testing in a number of key patient 'sub-groups'. For example, it is expected that a range of participant sub-groups meeting the study inclusion criteria will include patients with pre-existing diabetes, end-stage renal failure and iatrogenic immunosuppression;
- To quantify the use of next-generation IGRAs (that have high diagnostic sensitivity) compared to existing commercially-available assays;
- To analyse samples and thereby determine whether there is a genetic component which might determine severity of disease progression, via basic DNA analysis; and
- To determine the sensitivity, specificity, positive and negative predictive values of the two IGRAs as applied to bronchoalveolar lavage samples in patients with suspected pulmonary TB who are sputum smear-negative.

## 5. STUDY DESIGN

#### 5.1 Patient recruitment

A prospective multi-centre cohort study will be conducted in the UK (in routine clinical practice) of 1,012 adults ( $\geq$  16 years old) presenting with suspected active tuberculosis at either NHS out-patient or in-patient services within participating hospitals in London, Leicester, Birmingham and Oxford. Please see appendix A, for further clarification.

Patients will be recruited at the point of diagnostic work-up in secondary care, before a confirmed diagnosis has been determined. Thus, potential participants for the study will be indentified at this point. The study population is representative of the national tuberculosis burden in terms of ethnic mix and range of co-morbidities and will include sufficient numbers of HIV-infected patients to reliably

determine the role of IGRAs in this key population. The participating hospitals chosen do not routinely use IGRAs in their diagnostic work-up of suspected TB, and it is expected that this will assist in minimising the influence of IGRA results on the attending clinicians' diagnoses which could otherwise bias the evaluation of IGRA accuracy.

### 6. PARTICIPANT ENTRY

#### 6.1. Pre-registration evaluations

Potential participants (patients presenting at participating NHS centres) will be referred to a TB Research Nurse by the attending clinician (see table below, detailing TB diagnostic criteria). A second participant screening process will then be carried out by the TB Research Nurse, to ensure that participants meet the set inclusion criteria. To be included in the study, participants will need to be aged 16 years-of-age or over and present with suspected active TB (pulmonary or extra pulmonary), at either an inpatients or outpatients department.

**Table 1.0** Pre-defined composite reference standard for active tuberculosis, validated in a prospective UK study in routine practice.

Diagnostic Category	Criteria
1: Culture-confirmed tuberculosis	Microbiological culture of Mycobacterium tuberculosis and suggestive clinical and radiologic findings
2: Highly probable tuberculosis	M. tuberculosis culture negative but clinical and radiologic features highly suggestive of tuberculosis and unlikely to be caused by other disease and supportive histology and/or cytology if available and a decision to treat has been made and appropriate response to therapy
3: Clinically indeterminate	A final diagnosis of tuberculosis was neither highly probable nor reliably excluded with no alternative diagnosis and the patient was not subsequently diagnosed with TB within 6 months
4: Active tuberculosis excluded	All microbiological samples smear and culture negative and a definite alternative diagnosis identified and the patient was not subsequently diagnosed with TB within 6 months

During the second participant screening process, the TB Research Nurse will also determine whether to exclude participants from the study. The exclusion criterion includes a participant being aged less than 16 years-of-age, any previous treatment for TB, or an inability to provide informed consent.

If the TB status (or any other clinically relevant details) of each potential participant is seen to be adherent to the study inclusion/exclusion criteria, then he or she will be asked by the TB Research Nurse to ascertain whether or not they are willing to take part in the study, in accordance with good clinical practice (GCP). Each participant will be provided with an information sheet and a verbal description of the research study, why they have been approached and informed that participation is voluntary. When a participant has been given adequate time to reflect upon and consider participation in this study and only when they have agreed to take part, will they be asked to read, sign and date a consent form. The form will be signed in the presence of a TB Research Nurse, who will countersign the consent form. Three copies of the consent form will be made; a copy will be kept in the research file, a copy given to the patient and a copy put into the participant's medical notes.

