## **10. STATISTICS AND DATA ANALYSIS**

#### 10.1 The study diagram

A study diagram has been produced to show participant/patient numbers (estimated) for the study. Please see figure 2.0 below, which should be read in conjunction with the figure in appendix A.

Figure 2.0 Participant numbers - estimates

**a.** Estimated 200 HIV co-infected patients with suspected ATB to be recruited during study arise from the initial overall population of TB suspects presenting at Consortium hospitals. The corresponding study flow diagram for the subgroup would be the same as this study flow diagram, with proportionally smaller numbers. The only difference being that 62% of HIV TB suspects will be recruited and 50% of HIV TB suspects are expected to have a final diagnosis of ATB.

**b.** Proportion of suspects recruited determined by the number of days per week that TB Research Nurses attend participating hospitals – roughly 3 to 4 days at each Unit – enabling a recruitment rate of 34% of TB suspects without ascertainment bias.

c. Exclusion of ATB requires definite alternative diagnosis/absence of TB over 6 months follow-up.

d. Estimates based on average culture positive rates.

e. Estimates based on the study refereed to as Dosenjah et al in Annals of Internal Medicine.

Source: Detailed Project Description (Part II), page 18.

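### The claim of a 34% sample free of ascertainment bias is not secured by an entry rule that depends on clinician referral

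*Protocol*

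**What the plan says.** **Timing.** Section 5.1: "Patients will be recruited at the point of diagnostic work-up in secondary care, before a confirmed diagnosis has been determined".

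**Route.** Section 6.1: potential participants "will be referred to a TB Research Nurse by the attending clinician (see table below, detailing TB diagnostic criteria". A research nurse then screens them. The criteria listed there are age 16 or over and suspected active TB, with exclusion for younger age, previous TB treatment or inability to consent. The consent step that follows opens: "If the TB status (or any other clinically relevant details) of each potential participant is seen to be adherent to the study inclusion/exclusion criteria".

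**The table.** The only table in section 6.1 is Table 1.0, captioned "Pre-defined composite reference standard for active tuberculosis, validated in a prospective UK study in routine practice". Category 1 needs a positive culture. Category 2 needs that "a decision to treat has been made and appropriate response to therapy". Categories 3 and 4 need that "the patient was not subsequently diagnosed with TB within 6 months".

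**Sampling claim.** Figure 2.0 note b, section 10.1, says the recruited proportion is determined by the days that nurses attend, roughly 3 to 4 a week at each unit, "enabling a recruitment rate of 34% of TB suspects without ascertainment bias".

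**Use.** Section 10.2 places the main clinical utility of the tests in their NPV and says that this depends on sensitivity and on TB prevalence in those tested.

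**The concern.** Sampling by attendance day avoids ascertainment bias only if two things hold: the days are unrelated to the kind of patient seen, and every eligible suspect on those days is approached. The protocol gives the first as its reason and does not state the second. Under section 6.1 a patient reaches the nurse through a clinician's referral, and no section asks for all or consecutive suspects, or for a record of those not referred.

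The pointer to Table 1.0 adds to this. Taken literally, it asks the referring clinician to think in terms of final diagnostic categories at a point when, under section 5.1, none should be established. The mention of TB status at nurse screening has the same fault, because TB status is what the study sets out to determine.

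If referral were selective, the cohort's prevalence and case mix would differ from those of suspects in routine practice. PPV and NPV would then describe referred patients, and sensitivity and specificity could move through spectrum effects. No later analysis can recover suspects who were neither referred nor logged.

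**Working it through.** **1. The plan's own sample size reproduces.** Inputs from section 10.2: sensitivities 85% and 75%, two-sided 5%, 90% power, prevalence 40%, independent errors.
- Discordant proportion = 0.85 × 0.25 + 0.75 × 0.15 = 0.325; difference = 0.10.
- TB cases = 0.325 × (1.960 + 1.282)² / 0.10² = 341.5, rounded up to 342.
- Patients = 342 / 0.40 = 855, as stated.

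The sample size is not in dispute. It does rest on prevalence: the same 342 cases need 342 / 0.30 = 1,140 patients at 30% and 342 / 0.50 = 684 at 50%.

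**2. Do attendance days alone give 34%?** Assume that suspects present evenly over the week.
- Five-day week: 3/5 = 60% to 4/5 = 80%.
- Seven-day week: 3/7 = 43% to 4/7 = 57%.
- Share of suspects present on nurse days who are then recruited: 34/60 = 57% to 34/80 = 43% (five-day), or 34/43 = 79% to 34/57 = 60% (seven-day).

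On either basis a further fraction, from about a fifth to more than half, is lost after attendance is counted. Consent, eligibility and referral are candidates. So is the denominator: section 12.3 says that some hospitals recruit only HIV-positive patients, so HIV-negative suspects there may count among those not recruited. Figure 2.0 is not available and may show some of these steps. This is therefore supporting evidence only.

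**3. Can Table 1.0 be used at referral?** Section 5.1 requires entry "before a confirmed diagnosis has been determined". Category 1 is itself a confirmed diagnosis, category 2 needs response to therapy, and categories 3 and 4 need a 6-month outcome. No category can be assigned at entry to a patient who meets section 5.1.

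**4. What a prevalence shift would do to NPV.**

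NPV = (1 − p) × spec / [(1 − p) × spec + p × (1 − sens)]

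Sensitivity is 85% (section 10.2). The protocol gives no specificity, so 60%, 75% and 90% are assumed. For specificity 75%:
- p = 0.40: 0.450 / (0.450 + 0.060) = 88.2%
- p = 0.46: 0.405 / (0.405 + 0.069) = 85.4%, a fall of 2.8 points
- p = 0.50: 0.375 / (0.375 + 0.075) = 83.3%, a fall of 4.9 points
- p = 0.30: 0.525 / (0.525 + 0.045) = 92.1%, a rise of 3.9 points

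| Assumed specificity | NPV at 40% | Change at 46% | Change at 50% | Change at 30% |
|---|---|---|---|---|
| 60% | 85.7% | −3.3 | −5.7 | +4.6 |
| 75% | 88.2% | −2.8 | −4.9 | +3.9 |
| 90% | 90.0% | −2.4 | −4.3 | +3.3 |

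The 46% is itself an assumption: it arises if a share x = 10% of participants were enrolled with TB already established, 0.40 × (1 − x) + x = 0.46. Reaching 50% this way needs x = 0.10 / 0.60, about 17%.

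**5. Scale against sampling error.** At specificity 75% and prevalence 40%, 855 patients give 855 × 0.51 = 436 test-negatives. The standard error of NPV is √(0.882 × 0.118 / 436) = 1.54 points. The 2.8-point fall is about 1.8 standard errors.

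**The case against.** The eligible population is the same wherever the protocol states it: adults with suspected active TB and no earlier TB treatment. Sections 5.1, 6.1 and note b give a timing, a route and a sampling fraction, which can all hold together. A reader might infer that the population is defined in three incompatible ways; the text does not support that.

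The caption of Table 1.0 and the use of its categories in section 10.3 show that it is an outcome classification, so the parenthesis in section 6.1 is most naturally a misplaced cross-reference. A reader might also infer that patients with proven TB would be enrolled. Section 5.1 bars a confirmed diagnosis, and the exclusion for previous treatment removes anyone who has already responded to therapy. The exclusion list in section 6.1 does not itself repeat the bar on a known diagnosis, so restating it there is useful, but this is a small gap.

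Clinician referral is also compatible with every suspect on a nurse day being referred, in which case note b would hold. And the plan does not rest on NPV alone: likelihood ratios are planned, the powered comparison is of paired sensitivities in the same patients, and the data monitoring committee reviews TB and HIV prevalence.

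All of this stands, and it limits the point. It does not supply the missing condition. Note b asserts a property that the written entry rule does not secure, and monitoring prevalence among those enrolled cannot show who was not referred.

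**Conclusion.** The point holds in a limited form. The claim of no ascertainment bias is unsupported as written, because entry runs through clinician referral with no all-comer or consecutive requirement, and attendance days alone do not yield 34%. The Table 1.0 pointer conflicts with section 5.1 and needs correcting, though it is probably an editorial slip.

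The documents do not show that referral will be selective, nor in which direction. Over assumed specificities of 60-90%, a prevalence of 46% would lower NPV by 2.4 to 3.3 points, 50% would lower it by 4.3 to 5.7, and 30% would raise it by 3.3 to 4.6. These figures show how sensitive NPV is to prevalence; they do not estimate a bias. It is tempting to quote the move to 50% as a shift of about three standard errors, but in the scenario above that needs about 17% of participants to enter already diagnosed, against section 5.1.

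The change is worth making because it is cheap, it protects the measure that the protocol puts first, and it cannot be made good after recruitment.

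**What to change.** - In section 6.1, state that every consecutive patient under work-up for suspected active TB on a nurse attendance day is referred or approached, and repeat from section 5.1 that no diagnosis is confirmed at consent.
- Keep a simple log of suspects seen on those days but not enrolled, so that the claim in note b can be checked.
- Move the pointer to Table 1.0 to the place where final outcomes are classified, and replace the mention of TB status at nurse screening with suspected active TB.
- If selective referral has to remain, delete the statement about ascertainment bias from note b.

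The cost is wording in sections 6.1 and 10.1, plus slightly more screening time for nurses who are already on site.

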#### 6.2 Withdrawal criteria

Participants may withdraw from the study at any time, if they so desire. Assurance will be provided by the TB Research Nurse that any such refusal will not affect the care they are provided with, in any way. In accordance with GCP, participants who withdraw will not be required (nor asked) for a reason why they have decided to do so. Participants can also be removed from the study if a research investigator (or other member of the research team) considers that this is an appropriate course of action.

## 7. STUDY PROCEDURES

Blood taking (venepuncture) procedures will be carried out during the study period. The frequency and timing of blood taking procedures will be at three set time intervals: the first visit, time nought (T0); 2 months (2M) after T0, and finally 6 months (6M). Follow-ups, in addition to the set time intervals, may be carried out, if clinically indicated. A 35ml blood sample will be taken at each time point – this will be used for IGRA testing (ELISpot and ELISA based) and for storage (PBMCs and serum) in the bio-repository; please see figure 1.0 (page 12) for further clarification.

#### 7.1. Blood samples

[figure not shown]
A 35ml quantity specimen of blood will be collected from all consenting participants for IGRA testing; residual sample will be stored to repeat the small number of indeterminate results expected and for future research. PBMCs will be stored in a liquid nitrogen tank and serum and plasma will be stored in a -80°C freezer at the Tuberculosis Research Unit (led by [name]) at Imperial College London. On the same day as sample collection, blood samples will be transported by either the Research Nurses or by courier in appropriate UN-type approved packaging to the Clinical Immunology Laboratory at Imperial College London (TB Research Unit) at St. Mary's Hospital, for testing.

Blood samples will be taken at the same time as a participant's routine clinic appointment. Quantity of taken bloods, per tube, will comprise of the following: QFN (3ml), PBMCs (28ml) and Serum (3ml) with PaxGene tube (1ml) all stored within the Clinical Immunology Laboratory.

#### 7.2. Diagnostic Bronchoscopy

In patients with sputum smear negative pulmonary TB, diagnostic bronchoscopes are performed and collection of BAL (BronchoAlveolar Lavarge) is obtained as part of routine clinical care. The bronchoscopic procedure, along with collection of BAL, will occur in the endoscopy suite at St. Mary's Hospital, in accordance with set clinical practice guidelines. In cases where an amount of BAL is left over, after the procedure, an aliquot from the sample will be cryopreserved and stored in the research bio-repository for subsequent testing by IGRA. No additional BAL will be taken for this research study, and BAL samples will only be used for research if there is any left over after the procedure. The BAL sample consent is covered under the consent form, as "tissue samples". However, patients will still be informed if a surplus BAL sample is to be taken for this research study.

#### 7.3 Sample analysis

Each participant's sample will be tested with the two existing commercially-available IGRA tests: the ELISA-based Quantiferon-TB Gold in-tube (Cellestis Inc, Carnegie, Australia) and the ELISpot-based T-SPOT.TB (Oxford Immunotec Ltd, Abingdon, UK). All tests will be conducted and interpreted using manufacturers' instructions for processing the samples and scoring of assays.

ELISpotPLUS 1, which has enhanced sensitivity (described in reference 1), will also be carried out on blood samples from all participants in real-time and in parallel with the commercial assays, with results reported as part of the study. Bronchoalveolar lavage (BAL) will be carried out as part of the routine work-up of patients with suspected pulmonary TB with negative sputum smear results (estimated at approximately 200 BAL samples from our overall study population, based on HPA data on prevalence of sputum-smear-negative pulmonary TB [HPA 2008]); an aliquot from these samples will be cryo-preserved in the Research Tissue (TB) biobank and the ELISpot-based IGRA will subsequently be performed on thawed mononuclear cells in the category 3 biosafety containment facilities at Imperial College London.

A bio-repository of residual plasma and mononuclear cells will also be created to enable evaluation of next-generation IGRAs. These assays will be funded, carried out and reported separately from this research study. ELISpot incorporating promising new *M. tuberculosis* antigens that enhance diagnostic sensitivity without compromising specificity will be carried out on cryo-preserved mononuclear cells. ELISA to measure a novel chemokine, IP-10 (and potentially other cytokines) will be carried out on stored stimulated supernatants from the Quantiferon Gold in-tube assays. The large study sample size and stringent design will allow calculation of robust estimates of the sensitivity, specificity and negative and positive predictive values of these next-generation assays on blood and BAL samples. See appendix A, which shows a diagram of the logistical flow chart for sample

## 8. ADVERSE EVENTS

#### 8.1. Definitions

Adverse Event (AE): any untoward medical occurrence in a patient or clinical study subject.

Serious Adverse Event (SAE): any untoward and unexpected medical occurrence or effect that:

- Results in death
- Is life-threatening refers to an event in which the subject was at risk of death at the time of the event; it does not refer to an event which hypothetically might have caused death if it were more severe
- Requires hospitalisation
- Results in persistent or significant disability or incapacity
- Is a congenital anomaly or birth defect

Medical judgement should be exercised in deciding whether an AE is serious in other situations. Important AEs that are not immediately life-threatening or do not result in death or hospitalisation but may jeopardise the subject or may require intervention to prevent one of the other outcomes listed in the definition above, should also be considered serious.

#### 8.2. Blood venepuncture risks

The potential risk, as with any other blood sample venepuncture procedure, is a small chance of some bruising and tenderness around the area. When bruising does occur, the tenderness (typically) lasts for between two and four days after completing the procedure.

#### 8.3 Reporting procedures

All adverse events should be reported. Depending on the nature of the event the reporting procedures below should be followed. Any questions concerning adverse event reporting should be directed to the Chief Investigator in the first instance.

#### 8.3.1 Non serious AEs

All such events, whether expected or not, should be recorded.

#### 8.3.2 Serious AEs

An SAE form should be completed and faxed to the Chief Investigator and the Sponsor within 24 hours. All SAEs should be reported to the North West London REC1 Research Ethics Committee where in the opinion of the Chief Investigator, the event was:

- 'Related', ie resulted from the administration of any of the research procedures; and
- 'Unexpected', ie an event that is not listed in the protocol as an expected occurrence

Reports of related and unexpected SAEs should be submitted to ethics, the sponsor and the R&D office within 15 days of the Chief Investigator becoming aware of the event, using the NRES SAE form for non-IMP studies.

#### Contact details for reporting SAEs [contact] for the attention of [name] Please send SAE forms to: [name] [contact] (Monday to Friday: 09.00 to 17.00)

## 9. ASSESSMENT AND FOLLOW-UP

#### 9.1 Study participants

Study participants will have the opportunity to be seen beyond the set time periods (see section 7.0) if either they request this or a clinician decides that there is a clinical reason to do so. In this way participants can be assessed regularly by the investigating team, with any potential or actual adverse events detected rapidly. Participants meeting the criteria for a serious adverse event (see section 8.0) will be offered prompt treatment as appropriate.

Standard hospital follow-up will be in accordance with local hospital procedures. When the study is completed, study participants will not be routinely followed-up by the research study team; participants will return to the care of their GP (or other healthcare professional, as appropriate) upon completion of the study.

#### 9.2 Test Results and Further Action

[figure not shown]
IGRA results of blood samples taken for the study from patients suspected of TB will be entered into the database by the Research Assistants for analysis. These results are for this specific study only and will not be made available for clinical use. Although IGRA testing is not common practice for HIV-negative patients suspected of TB in the hospitals of our consortium and is not currently recommended for HIV-positive patients suspected of TB, any case-by-case IGRA testing requested by the attending clinician will run in parallel and these results will not be recorded or analysed in this study. IGRAs are not currently recommended in HIV-infected patients with suspected TB by current guidelines because of limited data, which highlights the importance of this study.

